7.1. Criteria for inclusion of subjects

Patients must meet ALL of the following criteria to be included in the study:

- 1) Over 18 years old
- 2) Inpatient
- 3) Diagnosis of SARS-CoV-2 infection confirmed by RT-PCR or antigen.
- 4) Computed tomography (CT) evidence of lung involvement attributed to COVID infection is presented. Patients in whom CT is not performed should have suspicion of pulmonary involvement by clinically with compatible or suggestive simple radiology.
- 5) Requires supplemental oxygen by basal saturation $\leq 93\%$ (with ambient O₂, 21%)

7.2. Criteria for excluding subjects.

Patients who present ANY of the following criteria may not be selected to participate in this study:

- 1) The patient's situation is so serious that the doctor responsible thinks he could die in the next 24 hours.
- 2) Patients require at randomization one of the following 4 ventilatory supports:
 - a) High oxygen flow devices.
 - b) Non-invasive mechanical ventilation.
 - c) Invasive mechanical ventilation.
 - d) extracorporeal membrane oxygenation (ECMO).

- 3) The patient is or has been on treatment in the last 2 weeks prior to randomization with glucocorticoids or inflammation-modifying drugs, both conventional (thiopurines, cyclophosphamide, cyclosporine, tracolimus, leflunomide, methotrexate, mycophenolate mofetil / mycophenolic acid, sulfasalazine, hydroxychloroquine or chloroquine) and synthetic or biological directed against therapeutic targets (abatacept, belimumab, CD-20, IL1, IL6, IL12.23, IL-23, IL-17, TNF, integrin α4β7 or Janus kinase inhibitors JAK). Patients who are only on maintenance therapy with corticosteroid doses less than or equal to 7.5 mg of prednisone or equivalent per day will not be excluded.
- 4) The patient is pregnant or nursing.
- 5) The patient has stage 4 or 5 chronic kidney disease (rCC <30 ml/min).
- 6) Moderate to severe dementia at the discretion of the investigator.
- 7) Hypersensitivity to any of the active ingredients or to any of the excipients included in its formulation.
- 8) Untreated systemic infections not caused by COVID-19.
- 9) Stomach ulcer or duodenal active.
- 10) Recent vaccination with live vaccines.
- 11) There is another infection or disease that explains the lung disorder
- 12) Inability of the patient to understand the study or sign the informed consent unless a consent delegated to a legal representative is made.
- 13) Active participation in another clinical trial in the past 15 days.

7.3. Criteria for withdrawal of subjects.

- Voluntary patient abandonment: patients have the right to withdraw from the study at any time and for any reason, being able to express it personally or through their representative.
- By medical criteria (safety and efficacy):
 - that it is necessary to adopt new treatments due to the presence of serious adverse events that may be related to the use of corticosteroids such as severe infection of bacterial origin, etc.

- the deterioration of this is severe and it is considered necessary to replace the administered corticosteroid or initiate additional immunosuppressants or immunomodulators.
- That there is scientific evidence that supports the administration of new treatments that change the prognosis of patients and force them to modify the standard treatment of these.
- For non-compliance or violation of the rules contained in the protocol: when the patient no longer complies with the rules or procedures established in this protocol or there is loss of follow-up.

All patients who, regardless of the cause and stage of the study in which they are, prematurely and permanently discontinue treatment or follow-up, should complete the premature withdrawal visit, which will take place within 24-48 hours of becoming aware of withdrawal.

7.4. Premature discontinuation of the Study.

This study may be temporarily interrupted or terminated prematurely if in the opinion of the sponsor there is sufficient reasonable cause. The investigator will receive written notice that the terminating party documents the reason for the suspension of the study.

The circumstances justifying the suspension of the present study include, but are not limited to:

- (a) Identification of unforeseen, substantial or unacceptable risks to patients.
- (b) Inability to enroll an acceptable number of patients.
- (c) Insufficient compliance with the requirements of the protocol.
- d) Plans for modification, suspension or discontinuity of the development of the study drug.
- e) Administrative reasons that the promoter could not solve with the health authorities.
- f) The study is interrupted if scientific evidence appears to support the administration of new treatments that change the prognosis of patients and force them to modify the standard treatment of these.

A safety rule to stop the trial is to find significant differences in efficacy endpoint or adverse event variables in interim analyses. The significance level established for stopping the test is $p<0.01$ for safety and $p<0.001$ for efficiency(Haybittle-Peto limit)¹³.

If the trial ends early or is suspended for any reason, the investigator shall promptly inform the trial subjects, ensuring appropriate treatment and follow-up of the trial and, where required by applicable law, inform the regulatory authority.

If the investigator terminates or suspends a trial without the prior agreement of the sponsor, he or she shall promptly inform the institution, and the investigator/institution shall promptly inform the sponsor and the CEIm and provide them with written justification for the cause of such termination or suspension.

If the sponsor terminates or suspends a trial, the investigator must inform the Institution where the trial is conducted and the investigator/institution must promptly inform the CEIm by providing written justification of the reasons for the termination or suspension.

If the Ethics Committee (CEIm) terminates or withdraws the favourable opinion of a trial, the investigator shall inform the institution and the investigator/institution shall promptly inform the sponsor of this fact and provide written justification as to the cause of such termination or suspension.

8. Description of the treatment.

8.1. Characteristics of the Research Product

Methylprednisolone boluses are currently a common treatment in diseases with a serious component of infamatio such as lupus nephritis. That is why its application in the inflammation phase of COVID could be useful, since these patients have a severe inflammatory profile. The response to intermediate doses of dexamethasone suggests a possible effect of treatment with higher doses.

The risks of corticosteroid treatment at the bolus dose in the short term are similar to those of administration of intermediate doses, with an increased risk of bacterial superinfection, baseline glycemic decompensation, or risk of psychosis or arousal. Use in cycles of a few days has no long-term side effects such as hypertension, dyslipidemia or osteoporosis.

The chosen pattern is the same as that used in acute inflammatory diseases, such as lupus nephritis. In case of lack of stock, it could be decided to use other glucocorticoid preparations in doses equivalent to that of methyl-prednisolone, according to the following table:

Table 2. Guidelines equivalences to methylprednisolone in different studiess.

Active substance	Agenda	Equivalence in methyl-prednisolone	Equivalence in prednisona
Dexamethasone	6 mg/24h	30 mg/24h	37,5mg/24h

Metilprednisolona	250mg/24h	N/A	312,5 mg/24h
Hidrocortisona	50-100mg/6h	20-40 mg/12h	25-50 mg/12h

Reference: doses calculated according to "Steroid Conversion Calculator", accessible in <https://www.mdcalc.com/steroid-conversion-calculator#evidence>

Patients with a confirmed diagnosis of SARS-CoV-2 who have pulmonary involvement and are at risk of developing adult respiratory distress syndrome will be included.

There are studies that have evaluated observationally the treatment with GC boluses in this pathology in which there seems to be a beneficial effect when compared with the usual treatment (Callejas-Rubio, Rodríguez-Baño, Ruiz-Irastorza).

8.2. Treatment groups and selected doses.

Patients continue with the treatment that is considered standard in their center and associate glucocorticoids in 2 possible regimens (group membership is done randomly)

- 1) RECOVERY guideline. Intravenous administration of 6mg of dexamethasone every 24h for 10 days. It can be given both orally and intravenously at the same dose
- 2) BOWLING GUIDELINE. Intravenous administration of 250mg of methylprednisolone every 24 hours for 3 days.

8.4. Concomitant treatments

8.3.1. Concomitant treatment allowed (Standard Treatment)

Although this is a pragmatic study in real practice and some degree of heterogeneity is accepted in standard treatment, minimum requirements are considered to be able to include patients in the study. Thus, as standard treatment is accepted:

- a) Supplemental oxygen. For use in patients with hypoxemia. The target for oxygen therapy should not exceed 92% in patients at risk of respiratory failure with hypercapnia and 96% in all other patients.
- b) Antibiotic treatment. Standard treatment protocols should not recommend the administration of empirical antibiotic treatment on a routine basis. Its administration should only be recommended when risk of bacterial pneumonia is considered as co-infection. The antibiotic regimen will correspond to the usual treatment guide of the center.
- c) Prophylaxis or thromboembolism treatment with low molecular weight heparins. Thrombotic prophylaxis is recommended in all admitted patients and the use of therapeutic doses in patients with confirmed thromboembolic disease. The use of extended prophylaxis guidelines could be assessed according to the recommendations of the Spanish society of thrombosis and hemostasis.

- d) Remdesivir. The use of remdesivir is accepted if it is done according to the recommendations of the Ministry of Health.
- e) Other antiviral drugs or drugs that block viral activity. The protocols should not incorporate the following drugs: Hydroxychloroquine or chloroquine, lopinavir-ritonavir.
- f) Serum therapy. The use of serum therapy is allowed in those indications defined in the protocols.
- g) Other concomitant medications without antiviral or immunosuppressive effect (eg: antihypertensives, analgesics, lipid-lowering agents, antiplatelet agents,...). There is no limitation to the use of these drugs.

8.3.2. Concomitant treatments prohibited.

Other immunosuppressants. The concomitant use of other immunosuppressants is NOT allowed in the first 48 hours of evolution. If immunosuppressants are prescribed during the study, patients in whom they are initiated with the third or subsequent dose of CG should be maintained. The use of these drugs in these patients will be considered as an event.

9. Development of the study.

9.1. Study schedule.

Recruitment is planned to begin in December 2020.

The overall duration of the study is estimated at approximately 9 months, from the start of the recruitment period (6 months of recruitment) to the last follow-up visit (3 months of follow-up). This study is expected to be completed in September 2021.

9.2. Calendar of visits.

Processes to be carried out	SCR	Day 4-6	Day 12-16	Day 28	3 months	Premature withdrawal
Informed consent	X					
Inclusion criteria	X					
Randomization	X					
Medical history comorbidities	X					
Physical examination	X	X	X	X	X*	X*
COVID Clinical Evaluation	X	X	X	X	X	X
WHO scale of 10 categories	X	X	X	X	X*	X*
Concomitant medication	X	X	X	X	X	X
Biochemistry and blood count	X	X	X	X	X*	X*
Adverse events	X	X	X	X	X	X
Rx the TC	X		X		X*	X*
ECG	X					

* Only in case of being a face-to-face visit.

9.3. Description of the visits and the procedures to be carried out in each visit.

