9.3.1. Study visits

- Selection/Randomization.
- Day 4-6 (any day between 4 and 6).
- Day 12-16 (any day between the 12th and the 16th).
- Day 28 (window allowed: day 24 to day 30).
- 3 months (window allowed: ± 2 weeks). This visit can be made in person or by telephone at medical discretion, depending on the patient's condition and the usual practice of the center.
- Visit to discharge or premature withdrawal. This visit can be done in person or by telephone.

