9.3.2. Study Procedures

- **Chronopathology of COVID-19 infection.** During the screening visit, the date of onset of symptoms and the date of the first confirmatory diagnostic test

will be collected. In addition, if the diagnostic RT-PCR was not performed in the last 10 days, it will be necessary to repeat it and confirm the positivity.

- **Medical history comorbidities** (including hypertension, diabetes mellitus, dyslipidemia, heart failure, ischemic heart disease, stroke, chronic obstructive pulmonary disease, bronchial asthma, hypopnea sleep apnea syndrome, hypoventilation, chronic kidney disease, chronic liver disease, neoplasia, transplant, human immunodeficiency virus infection, autoimmune disease, dementia, smoker)
- **Clinical evaluation of COVID**, assessment of own symptoms, date of onset of symptoms and evolution of them.
- **WHO scale** of 10 categories (Annex 1).
- **Physical examination** (includes general assessment of the patient, degree of hydration, nutrition, vital signs and respiratory situation, cardiopulmonary auscultation, abdominal examination and a neurological assessment of alertness).
- **Concomitant medication** registration (start and end date, active substance and dose).
- **Biochemistry and blood count** (determination of blood count, coagulation with D-dimer, biochemistry including creatinine, ions, AST, ALT, BT, BD, LDH, PCR, ferritin, blood gases and IL-6).
- **Adverse events**, medication-related or non-medication-related.
- **Chest X-ray (X-ray) or Computed Tomography (CT)** (Brixia scale – Annex 1).
- **Electrocardiogram (ECG), according to** the usual practice of the center.
- Both the 3-month follow-up visit and the premature withdrawal visit can be done in person or by telephone. If the visit is carried out in person, in addition to the assessment of the COVID clinic, the registration of concomitant medication and the registry of adverse events, the following procedures would be carried out:
 - WHO scale of 10 categories (Annex 1).
 - Physical examination.
 - Biochemistry and blood count.

- Chest X-ray (X-ray) or Computed Tomography (CT) (Brixia¹² scale – Annex 1).

10. Study variables and parameters

10.1. Variable Principal:

- Death after 28 days

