10.2. Secondary Variables

- Admission to the Intensive Care Unit at 28 days
- Need for noninvasive mechanical ventilation or high-flow oxygen at 28 days.
- Need for mechanical ventilation and intubation at 28 days.
- Use of other immunosuppressive drugs.
- Time to discharge (days of hospitalization from start of treatment)
- Baseline at 3 months of treatment according to the WHO 10-category scale .

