ANNEX 1: Scales of measurement

A. Serious situation. WHO Proposal¹⁴

Patient status	Descriptor	Scale
	Not infected. No virus detected	0
Ambulant. Mild illness	Asymptomatic, independent, virus detected	1
	Symptomatic, independent	2
	Symptomatic, needs help	3
Hospitalized. Moderate disease	Hospitalized. Does not require Oxygen	4
	Hospitalized. Precise oxygen either by nasal glasses, or by conventional mask	5
Hospitalized. Severe illness	High-flow oxygen or noninvasive mechanical ventilation	6
	Mechanical intubation, $pO_2/FiO_2 \geq 150$ or $SpO_2/FiO_2 \geq 200$	7
	Mechanical intubation, vasopressors, or $pO_2/FiO_2 < 150$ ($SpO_2/FiO_2 < 200$)	8
	Mechanical intubation, $pO_2/FiO_2 < 150$ + vasopressors, dialysis, or ECMO	9
Deceased	Deceased	10

B. Severity scale Rx Brixia Score (0 to 18 points)¹².

Lung area	Normal	Interstitial infiltrate	Interstitial and alveolar infiltrate with predominance of the former	Interstitial and alveolar infiltrate with predominance of the second
Top right	0	1	2	3
Middle right	0	1	2	3
Lower right	0	1	2	3
Top left	0	1	2	3
Middle left	0	1	2	3
Bottom left	0	1	2	3
Total				

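### The 3-month WHO-scale secondary endpoint is scored only at face-to-face visits, so survivors followed by telephone have no score, and who is missing depends on health status and centre

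*Combined protocol and SAP*

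**What the plan says.** Section 10.2 (secondary variables) includes "Baseline at 3 months of treatment according to the WHO 10-category scale". The word baseline there reads as a translation of the patient's status at that time.

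The table in 9.2 marks the WHO scale without condition at screening, days 4-6, days 12-16 and day 28. At 3 months and at premature withdrawal it carries an asterisk, explained as "Only in case of being a face-to-face visit".

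Section 9.3.1 says of the 3-month visit: "This visit can be made in person or by telephone at medical discretion", and ties the choice to the patient's condition and the centre's habits.

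Section 9.3.2 gives the same rule in prose. The sentence beginning "If the visit is carried out in person, in addition to the assessment of the COVID clinic, the registration of concomitant medication" introduces a list of extra in-person procedures: the WHO scale, physical examination, laboratory tests and imaging.

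Section 11.3 plans frequencies and percentages for categorical variables. It names no specific analysis for this scale and no rule for patients without a score.

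**The concern.** A secondary endpoint dated at 3 months needs a value for every survivor who is reached at 3 months. Here a patient can complete the planned contact by telephone and still have no endpoint value. The stated reason for choosing the telephone includes the patient's condition, which is what the scale grades, and centre practice adds a second source of selection. The scored survivors would then not represent all survivors, and precision would be lost as well. At stake is the only efficacy variable in 10.2 that is dated at 3 months.

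**Working it through.** **Does any other text supply the score?**

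- The unstarred rows of 9.2 (COVID clinical evaluation, concomitant medication, adverse events) apply to telephone visits. In 9.3.2 the clinical evaluation is "assessment of own symptoms, date of onset of symptoms and evolution of them". That covers symptoms, but Annex 1 separates category 2 (independent) from category 3, "Symptomatic, needs help", and independence is not asked about.
- Section 11.2.3 lets data come from interview and the full medical history. Its record search is for patients who miss a visit and looks for events. A completed telephone visit is not a missed one, and no text derives a WHO score from records.
- Serious adverse event reporting (12.10) captures many deaths and readmissions, but stops 30 days after a subject leaves. Section 7.3 counts loss to follow-up as withdrawal. Deaths are therefore largely, not always, known.
- Under 7.3, patients who stop early "should complete the premature withdrawal visit, which will take place within 24-48 hours of becoming aware of withdrawal". That contact does not give 3-month status.
- Category 0 is "Not infected. No virus detected", and category 1 also refers to virus detection. The 9.2 calendar has no virus test at 3 months, so 0 and 1 cannot be told apart in either mode.

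**Size, by illustration.** The plan states no figure for this endpoint, so there is nothing to reproduce. From 11.1: 145 per arm, with 28-day mortality of 23% and 10%. Assumptions: these mortalities hold to 3 months; a share u of survivors is unwell (a working label that the plan does not define); telephone use is t_u in unwell and t_w in well survivors.

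Survivors: 145 × 0.77 + 145 × 0.90 = 242 of 290.

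Unscored share = u·t_u + (1−u)·t_w.
Observed unwell share = u(1−t_u) / [u(1−t_u) + (1−u)(1−t_w)].

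| u | t_u | t_w | Unscored | Observed unwell share |
|---|---|---|---|---|
| 0.20 | 0.30 | 0.70 | 0.06 + 0.56 = 62% (about 150) | 0.14/0.38 = 37% |
| 0.20 | 0.70 | 0.30 | 0.14 + 0.24 = 38% (about 92) | 0.06/0.62 = 10% |
| 0.30 | 0.30 | 0.80 | 0.09 + 0.56 = 65% | 0.21/0.35 = 60% |
| 0.10 | 0.80 | 0.30 | 0.08 + 0.27 = 35% | 0.02/0.65 = 3% |

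The unscored share is a weighted mean of t_u and t_w, so with both between 30% and 80% it also runs from 30% to 80%. The last two rows are the extremes of the observed share for u between 10% and 30%.

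**Effect on the comparison of arms, with the same selection in both.**

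- If mortality and u are equal in the two arms, the observed distributions are equal. A true null stays null.
- The odds ratio between any two single categories is unchanged, because the selection factors cancel. Dead against well, u = 0.20: true (0.23/0.616)/(0.10/0.720) = 2.69; with the first row's selection (0.23/0.1848)/(0.10/0.2160) = 2.69.
- Percentages do change if known deaths are kept and unscored survivors dropped. With 40% telephone use regardless of health, deaths are 0.23/(0.23 + 0.77 × 0.6) = 33% against 0.10/(0.10 + 0.90 × 0.6) = 16% of scored patients, instead of 23% against 10%.
- Cumulative splits change too. For unwell or dead, u = 0.20, the true odds ratio is (0.384/0.616)/(0.280/0.720) = 1.60. The first row's selection gives (0.3378/0.1848)/(0.2260/0.2160) = 1.75. The plan names no such split; this shows only that the distortion exists.

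**The case against.** The case for leaving this alone has weight. The variable is the last of six in 10.2, and none of the secondary objectives in 5.3 names 3-month status. Telephone visits still collect symptoms, adverse events and medication, and 11.2.3 gives access to the full history, so categories 4 to 10 can largely be reconstructed. Every telephone rate above is assumed. All of this stands, and it limits the importance of the point. It does not supply the missing score: the table and the prose agree that the scale is in-person only, so a misplaced asterisk is an unlikely explanation.

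A reader might infer more than the documents support:

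- **That the endpoint will show a false treatment effect.** This would need visit mode to be chosen differently by arm. It is possible in an open-label trial, but nothing in the documents shows it.
- **That the direction of the distortion is known.** The protocol does not say whether sicker or healthier patients are called in, and the two patterns pull in opposite directions.
- **That nothing is known about telephoned patients.** The main loss is in categories 0 to 3, above all the split between 2 and 3.
- **That the main result is affected.** Death at 28 days and the unstarred day-28 WHO score do not depend on this rule.

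**Conclusion.** The point holds in this limited form and should be corrected. As written, 3-month WHO status is unscored for every survivor followed by telephone, and the missingness depends on centre and on the health status being measured. This follows from the text alone. The size does not: a true 20% unwell share appearing as 37% or 10%, and 30% to 80% of survivors unscored, rest on assumed telephone rates and on 28-day planning mortality carried to 3 months. With equal selection in both arms, a null stays null and odds ratios between single categories survive. The percentages that 11.3 plans to report, and any cumulative split, are distorted if known deaths are kept and unscored survivors dropped.

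**What to change.** - In 9.2, remove the asterisk from the WHO-scale row at 3 months. In 9.3.2, take the scale out of the in-person list for that visit. Leave physical examination, laboratory tests and imaging in-person only.
- Score the scale at the 3-month contact in either mode, with one added question on independence.
- Score known deaths 10. Where there is no contact, including after withdrawal, use the medical record if consent allows.
- Report categories 0 and 1 together.
- Record the visit mode and report the number unscored by arm. In 11.3, state how unscored patients are handled and add a sensitivity analysis with best-case and worst-case placement. The worst case should not assume that they are ambulatory, since a patient with neither contact nor record may have been readmitted.

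The cost is two text edits, one question on a call that already asks about symptoms, one extra data field and a little more analysis. The downside is that the ambulatory categories would be assessed partly in person and partly by telephone. Some withdrawn patients may still have no score.
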